#### **10.4.4. Recurrent malignancy**

For purposes of this study, recurrent malignancy after allo-SCT is defined as clinical or histopathologic evidence demonstrating the presence of any malignancy considered as the indication for transplant. Recurrent malignancy after allo-SCT will also be defined as any post-transplant intervention not routinely used to prevent the development of overt recurrence, prompted by laboratory evidence of persisting malignant cells but without clinical or histopathologic evidence of recurrence. Recurrent malignancy after a non- myeloablative or reduced intensity conditioning regimen will be defined as any ad hoc post- transplant intervention intended to induce a donor immune-mediated anti-neoplastic effect, prompted by clinical or laboratory evidence indicating the need to eliminate persistent or progressive malignancy. Examples of such interventions include accelerated withdrawal of systemic immunosuppressive medications and donor lymphocyte infusion.

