8.2.2 Secondary endpoints

- OS is defined as the time from first infusion of ATO to death, regardless of the cause
- FFS is defined as related death, progression, or initiation of a new systemic treatment for chronic GvHD
- PFS is defined as survival with no evidence of relapse or progression of the original disease

- Corticosteroids dosage and percentage of reduction in corticosteroids dosage at 6 and 12 months after diagnosis of chronic GvHD and treatment with ATO as first line treatment
- Quality of life parameters using FACT-BMT and Lee Symptom Scale scores at 6 and 14 weeks, 6, 9 and 12 months after first infusion of ATO
- Tolerability and safety of ATO

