12.4.3.4 Statistical analyses

A descriptive analysis will be conducted on the following parameters:

- Patients and transplant characteristics
- Primary and secondary endpoints

The toxicities rate will be calculated and will be given with their 95% confidence intervals.

The probabilities of survival will be estimated by the Kaplan-Meier method and by calculating the cumulative incidences for relapse/progression, and non-relapse mortality incidence.

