11.4.2.2 Survival analyses

a) Failure free survival

A survival analysis will be conducted to describe the occurrence of failure between the first infusion of ATO and Vi, with Vi={M6;M12}.

Derivation

Derived variables	Definition
Failure at Vi Calculated at Vi={M6;M12}	Defined as death, recurrent or progressive malignancy, or the initiation of a new systemic treatment for chronic GvHD. Systemic treatment are: Methotrexate, Rapamune, TLI, Extracorporeal photopheresis, Rituximab, Jakavi, Glivec, Prograf, Imurel or other medications specified into the CRF (Vi_RESP_FAIL and or Vi_RESP_FAIL_S)
Time calculation from first ATO infusion to failure at Vi Calculated at Vi={M6;M12}	If the event appears: the difference of date between the first ATO infusion and the first failure (expressed in months) is calculated. The event will be not censored. $(\text{Date of first ATO infusion} - \text{Date of first failure})/30.5$ If the event does not appear, the difference of date between the first ATO infusion and Vi (expressed in months) is calculated. The event will be censored.

The following table will be presented at M6:

FAS Population

(N = XX)

First time of failure between first ATO infusion and M6 (in months)	n/M (%) of events	n/N (XX.XX%)
	n/M (%) of censored	n/N (XX.XX%)

The Kaplan-Meier survival estimates will be plotted with the number of subjects at risk and 95% confidence limits.

These analyses will be also presented at M12.

b) Progression free survival

A survival analysis will be conducted to describe the occurrence of progression between the first infusion of ATO and Vi, with Vi={M6;M12}.

Derivation

Derived variables	Definition
Progressive disease at Vi Calculated at Vi={M6;M12}	Global progressive disease as define in Appendix 17.1
Time calculation from first ATO infusion to failure at Vi Calculated at Vi={M6;M12}	If the event appears: the difference of date between the first ATO infusion and the first progression (expressed in months) is calculated. The event will be not censored. $(\text{Date of first ATO infusion} - \text{Date of first progression})/30.5$ If the event does not appear, the difference of date between the first ATO infusion and Vi (expressed in months) is calculated. The event will be censored.

The following table will be presented at M6:

FAS Population		
(N = XX)		
First time of progression between first ATO infusion and M6 (in months)	n/M (%) of events	n/N (XX.XX%)
	n/M (%) of censored	n/N (XX.XX%)

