The Kaplan-Meier survival estimates will be plotted with the number of subjects at risk and 95% confidence limits.

These analyses will be also presented at M12.

c) Overall survival

A survival analysis will be conducted to describe the occurrence of death between the first infusion of ATO and Vi, with Vi={M6;M12}.

Derivation

Derived variables	Definition
Death at Vi Calculated at Vi={M6;M12}	Yes, if the death occurs between the first ATO infusion and Vi
Time calculation from first ATO infusion to death at Vi Calculated at Vi={M6;M12}	If the event appears: the difference of date between the first ATO infusion and the date of death (expressed in months) is calculated. The event will be not censored. (Date of first ATO infusion – Date of death)/30.5 If the event does not appear, the difference of date between the first ATO infusion and Vi (expressed in months) is calculated. The event will be censored.

The following table will be presented at M6:

FAS Population		
(N = XX)		
Death between first ATO infusion and M6 (in months)	n/M (%) of events	n/N (XX.XX%)
	n/M (%) of censored	n/N (XX.XX%)

The Kaplan-Meier survival estimates will be plotted with the number of subjects at risk and 95% confidence limits.

These analyses will be also presented at M12.

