- peau, yeux, œsophage, tractus gastro-intestinal supérieur et inférieur : augmentation 1 point ou plus sur échelle de 0 à 3 = progression SAUF si changement de 0 à 1 (progression non spécifique)
- Joint: augmentation d'1 point ou plus = progression
- bouche : changement de 2 points ou plus sur la somme des 3 sous-scores

- pour Lung, diminution de 10 % avec FEV1 à V1 < 75% . Dans le cas de FEV1 manquants, augmentation d'1 point ou plus *SAUF* si changement de 0 à 1 (progression non spécifique)

- pour Liver, si l'une des valeurs à M6 est au-dessus de la normale pour Bilirubine, ALAT ou PAL, la recherche d'une progression est effectuée : la différence M6 – V1 est calculée et si la différence est supérieure à 2*ULN, il y a Progression.

Global progressive disease : si au moins un site avec une progression

Mixed response: si **Progressive disease** sur au moins un organe et **Partial response** sur au moins un autre

Extraits du protocole :

Table 4. Response determination for chronic GvHD (extrait du protocole)

Organ	Complete Response	Partial Response	Progression
Skin	NIH Skin Score 0 after previous involvement	Decrease in NIH Skin Score by 1 or more points	Increase in NIH Skin Score by 1 or more points, except 0 to 1
Eyes	NIH Eye Score 0 after previous involvement	Decrease in NIH Eye Score by 1 or more points	Increase in NIH Eye Score by 1 or more points, except 0 to 1
Mouth	NIH Modified OMRS 0 after previous involvement	Decrease in NIH Modified OMRS of 2 or more points	Increase in NIH Modified OMRS of 2 or more points
Esophagus	NIH Esophagus Score 0 after previous involvement	Decrease in NIH Esophagus Score by 1 or more points	Increase in NIH Esophagus Score by 1 or more points, except 0 to 1
Upper GI	NIH Upper GI Score 0 after previous involvement	Decrease in NIH Upper GI Score by 1 or more points	Increase in NIH Upper GI Score by 1 or more points, except 0 to 1
Lower GI	NIH Lower GI Score 0 after previous involvement	Decrease in NIH Lower GI Score by 1 or more points	Increase in NIH Lower GI Score by 1 or more points, except from 0 to 1
Liver	Normal ALT, alkaline phosphatase, and Total bilirubin after previous elevation of 1 or more	Decrease by 50%	Increase by 2 × ULN

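### The SAP derives progression-free survival from cGvHD organ worsening alone, so death is not an event and the result can exceed overall survival

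*SAP*

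**What the plan says.** SAP 8.2.2 states: "PFS is defined as survival with no evidence of relapse or progression of the original disease". The protocol lists OS and PFS at 6 and 12 months (9.1.2) and names improving PFS as an objective (2.2), but does not define PFS.

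The derivation in SAP 11.4.2.2 b is narrower. It opens with "A survival analysis will be conducted to describe the occurrence of progression between the first infusion of ATO and Vi" and gives one event: "Global progressive disease as define in Appendix 17.1". Appendix 17.1 defines that state as "Global progressive disease : si au moins un site avec une progression", that is, progression in at least one site. The sites are the cGvHD organs: skin, eyes, mouth, gastrointestinal tract, joints, lung and liver. The time formula and the output table also refer only to first progression. A patient without the event is censored at the visit concerned, M6 or M12.

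The neighbouring derivations are explicit about other events. The FFS event in 11.4.2.2 a is "Defined as death, recurrent or progressive malignancy, or the initiation of a new systemic treatment for chronic GvHD". For OS in 11.4.2.2 c, "the difference of date between the first ATO infusion and the date of death (expressed in months) is calculated".

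**The concern.** The definition and the derivation describe different endpoints. The definition begins with survival, so a patient who has died cannot be progression-free. Under the derivation, a patient who dies before the visit without organ worsening is event-free and, read literally, is followed to a visit after death. If the original disease is the malignancy, a patient who relapses with quiet cGvHD is also event-free, while a patient in remission whose skin score worsens counts as a PFS event.

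The PFS objective would then be answered by time to cGvHD organ worsening under the name PFS. An endpoint defined as survival without progression can never lie above OS. This one can, and a reader of the report would have no warning.

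**Working it through.** **Inputs.** The PFS definition is from SAP 8.2.2, the event rules from SAP 11.4.2.2 a to c and Appendix 17.1, and the sample sizes from SAP 12.4.3.5 (21 required, 24 planned). The SAP gives no PFS figure to reproduce, and neither document gives event counts, so all counts below are assumptions.

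**Step 1. Which events count.**

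| Source | Death | Malignancy relapse or progression | cGvHD organ worsening |
|---|---|---|---|
| PFS as defined (8.2.2) | Yes | Yes, if it is the original disease | Only if cGvHD is the original disease |
| PFS as derived (11.4.2.2 b) | No | No | Yes, the only event |
| FFS as derived (11.4.2.2 a) | Yes | Yes | No, unless new systemic treatment starts |
| OS as derived (11.4.2.2 c) | Yes | No | No |

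Death is missing under either meaning of original disease.

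**Step 2. What original disease means.** The SAP does not say. Three passages point to the transplant indication. SAP 12.4.3.4 pairs relapse with non-relapse mortality ("by calculating the cumulative incidences for relapse/progression, and non-relapse mortality incidence"). Protocol 10.4.4 says "recurrent malignancy after allo-SCT is defined as clinical or histopathologic evidence demonstrating the presence of any malignancy considered as the indication for transplant". Protocol 8.3 ties tumour assessment to the underlying disease. Against this, Protocol 9.3 uses progressive disease as a cGvHD response category. The malignancy reading is therefore an inference, though the more natural one.

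The cGvHD reading does not rescue the derivation. Protocol 9.3 requires worsening without improvement in any other organ and keeps mixed response separate. Under Appendix 17.1, a mixed responder also meets global progressive disease and would count as a PFS event.

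**Step 3. Weight of one patient.** 1/24 = 4.2 points; 1/21 = 4.8 points.

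**Step 4. Effect of omitting death.** Let D be deaths without organ worsening and P survivors with organ worsening, with no other early loss:

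- OS = (N − D)/N
- PFS as derived = (N − P)/N
- PFS with death added as an event = (N − D − P)/N

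Derived PFS minus OS is (D − P)/N, so derived PFS exceeds OS exactly when D > P. It overstates the version with death added by D/N.

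| N | D | P | OS | PFS as derived | PFS with death added |
|---|---|---|---|---|---|
| 24 | 1 | 0 | 95.8% | 100% | 95.8% |
| 24 | 2 | 0 | 91.7% | 100% | 91.7% |
| 24 | 3 | 0 | 87.5% | 100% | 87.5% |
| 24 | 3 | 1 | 87.5% | 95.8% | 83.3% |
| 24 | 2 | 4 | 91.7% | 83.3% | 75.0% |
| 21 | 3 | 0 | 85.7% | 100% | 85.7% |
| 21 | 3 | 1 | 85.7% | 95.2% | 81.0% |

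Kaplan-Meier estimates at M6, with progressions placed at month 2 and deaths at month 3, give these values whether the deaths are censored at the visit or at the death date. If a progression follows the deaths, the two rules differ slightly. With N = 24, 3 deaths censored at month 3 and 1 progression at month 5, derived PFS is 20/21 = 95.2% instead of 23/24 = 95.8%.

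**Step 5. Effect under the malignancy reading.** Let d be patients with death or relapse but no organ worsening, and o patients with organ worsening only. Without early censoring, derived minus defined PFS is (N − o)/N − (N − d)/N = (d − o)/N. For d from 0 to 3 and o from 0 to 4, this runs from −4/24 = −16.7 to +3/24 = +12.5 points at N = 24, and from −4/21 = −19.0 to +3/21 = +14.3 points at N = 21.

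**The case against.** The best textual defence is SAP 12.4.3.2, which names progression and death together as events of interest. That sentence is a general censoring rule covering several endpoints, and it reads naturally as progression for PFS and death for OS. It adds no event to the 11.4.2.2 b table. At most it moves the censoring date, and derived PFS can still exceed OS.

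A second argument is that the authors meant cGvHD by original disease, since the only operational PFS text uses cGvHD progression. This cannot be excluded. It would remove the point about malignancy relapse, but not the omission of death.

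Third, the examples with P = 0 favour the criticism. That is fair. D > P is needed for PFS to exceed OS; on the grid in step 5, treating every d as a death and every o as a survivor, this holds in 6 of 20 combinations. The FAS also requires a completed first cycle and a Week 6 assessment (SAP 11.1), so deaths before then cannot enter the counts.

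Fourth, the consequences are limited. No test or decision rests on PFS, and OS and FFS still show deaths and relapses among FAS patients. This stands, and it limits the severity. The cumulative incidences promised in SAP 12.4.3.4 are a weaker safeguard, because the table and figure lists in SAP section 14 contain no such output.

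**Conclusion.** The concern holds. Followed exactly, the SAP would report as PFS a quantity that contradicts its own definition. The omission of death is certain. The omission of malignancy relapse depends on reading original disease as the transplant indication.

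The only size anchored in the documents is about 4.2 points per misclassified patient at N = 24, or 4.8 at N = 21. The direction and total depend on unknown counts. Omitting death or relapse raises the estimate, and counting organ-only worsening lowers it relative to the malignancy definition. This should be corrected, but it does not touch the primary endpoint or the trial's decision rule.

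**What to change.** In SAP 11.4.2.2 b, define the PFS event as the first of relapse or progression of the underlying haematological disease or death from any cause, and define original disease in 8.2.2 to match. If cGvHD progression is also of interest, report it under its own name with the progressive-disease definition of Protocol 9.3, and state how mixed responders are counted. If the sponsor did mean cGvHD, death must still be added before the result can be called PFS.

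Three clarifications belong in the same edit:

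- Refer to 12.4.3.2 from 11.4.2.2, so that event-free patients are censored at the earlier of the visit and the last information date.
- Reverse the subtraction in the three time formulas, which take the event date from the first infusion date and so give negative times.
- Align the FFS line in 8.2.2 with 11.4.2.2 a.

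The cost is SAP text and the matching programming. FFS and OS already need recurrence and death dates, and Protocol 8.3 asks for progression or relapse to be documented during follow-up. The CRF is not among the documents, so separately dated malignancy relapse should be confirmed. Tumour assessment follows centre practice, so the precision of relapse dates may vary between centres.

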Score = 2 : Bilirubine élevée (>1*ULN) mais <= à 3 mg/dL OR ALAT >= 5 UNL OR PAL >=5 UNL (non mentionné dans article NIH).

Score = 3 : Bilirubine élevée > à 3 mg/dL

Lung : si FEV1 >=80% et FEV1<70 à V1. et dans le cas où la valeur de FEV1 est manquante, si le score est égal à 0

M6_GVHD_A_LU_FEV1_V>= 80
 missing(M6_GVHD_A_LU_FEV1_V) and M6_GVHD_A_L=0
 M6_GVHD_A_L
 M6_GVHD_A_L_ABN

Calcul de réponse par organe :

Aucun calcul de réponse **par organe** (complète, partielle ou progression) n'est effectué si :

- « abnormalities present but explained entirely by non-GVHD documented cause » = Oui pour un organe à la visite considérée
- CR_*organe*, PR_*organe* et PD_*organe* sont alors mis à . (manquant)

Aucun calcul de réponse complète ou partielle **par organe** n'est effectué si :

- l'organe n'est pas atteint à V1 ou abnormalities present but explained entirely by non-GVHD documented cause » = Oui pour un organe à la visite V1.
- la progression est recherchée même si pas d'atteinte à V1
- CR_*organe* et PR_*organe* sont alors mis à . (manquant)

- **Partial response by organ:** en se basant sur les mêmes scores et en s'intéressant aux diminutions (ou augmentations) entre V1 (mêmes variables qu'indiquées précédemment mais qui commencent par « V1 » au lieu de « M6 ») et la visite considérée (M6, W6, W14, M9 ou M12)

- une diminution d'1 point pour les scores sur des échelles de 0 à 4 pour : Skin BSA, Skin features, Eyes, Joints, Gastro-oesophageal, Gastro-upper, Gastro-lower,
- une diminution de 2 points pour la somme des 3 sous-scores pour Mouth
- pour Lung, une augmentation entre V1 et la visite d'au moins 10% sur FEV1 avec FEV1 à V1 <70. Dans le cas de FEV1 manquants à V1 et ou M6, une diminution d'1 point sur le score 'lungs'
- pour Liver, (Bilirubine, ALAT ou PAL),
- si les valeurs à M6 sont en dessous des normales, la réponse est considérée Complète
- sinon la recherche d'une réponse partielle est effectuée : diminution de 50% de la valeur initiale
 Le ratio est calculé ainsi : $(M6-V1/V1)*100$ et si le ratio est inférieur à -50 (mais pas de progression pour une des autres valeurs), il y a une réponse partielle

Global Partial response: au moins une réponse partielle sur un organe et avec une absence de progression pour un autre site

- **Progressive disease by organ:**

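### The PFS event row in SAP 11.4.2.2 b) tests progression at the M6 or M12 visit, while the rest of the section describes first progression up to that visit; followed literally, it drops transient progressions and can only overstate PFS

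*SAP*

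**What the plan says.** The PFS derivation in SAP 11.4.2.2 b) has two rows. The first sets the event. It is labelled as progressive disease at Vi, carries the tag "Calculated at Vi={M6;M12" (M6 and M12, no other visit), and is defined as "Global progressive disease as define in Appendix 17.1". The second sets the time. If the event appears, "the difference of date between the first ATO infusion and the first progression (expressed in months) is calculated"; otherwise the patient is censored at Vi.

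SAP Appendix 17.1 works visit by visit. It compares baseline (V1) with one visit at a time: "et la visite considérée (M6, W6, W14, M9 ou M12". Global progressive disease needs at least one progressing site at the visit considered. No rule carries an earlier progression forward.

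The introduction to the same subsection is about an interval: "A survival analysis will be conducted to describe the occurrence of progression between the first infusion of ATO and Vi". The table shell is labelled in the same way, as the first time of progression from first infusion to M6. The overall survival row in 11.4.2.2 c) has the same visit tag but a cumulative definition: "Yes, if the death occurs between the first ATO infusion and Vi".

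**The concern.** For a time-to-first-event endpoint, whether a patient has had an event by Vi must depend on everything observed up to Vi. The event row asks instead about organ status at Vi. A patient who progresses at W14 and has improved by M6 has no event in the M6 analysis. A patient who progresses at M6 and has improved by M12 has an event in the M6 analysis and none in the M12 analysis.

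Transient progression is plausible here. The prednisone guideline (Protocol 6.2, SAP 9.3.6.2) provides for a dose increase when chronic GvHD flares, and a dose increase is not a failure (Protocol 9.3 and 10.4.3). A patient who progresses, has the steroid dose raised and improves would appear in neither PFS on the literal row nor FFS. At stake is the estimate of a named secondary endpoint, PFS at 6 and 12 months (Protocol 9.1.2), and the consistency of the M6 and M12 results with each other.

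**Working it through.** The documents give no PFS rate or event count, so there is no planned figure to reproduce. The check compares the text and then counts events under the two readings.

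**1. The passages side by side (SAP)**

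- 11.4.2.2 b), event row: status at Vi, for M6 and M12.
- 11.4.2.2 b), introduction, timing rule and table label: first progression from first infusion to Vi.
- 11.4.2.2 c), event row: any death from first infusion to Vi.
- 11.4.2.3 (corticosteroids): here the visit set is written out as W6, W14, M6, M9 and M12.
- Appendix 17.1: can be run at all five visits, one at a time.

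The timing rule mentions first progression but applies only if the event has appeared, and the event row decides that. So the timing rule alone does not bring back a progression that has resolved by Vi.

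**2. Assessments that the literal event row does not use**

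- M6 analysis: W6 and W14, that is 2 of 3.
- M12 analysis: W6, W14, M6 and M9, that is 4 of 5.

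**3. Event counts under each reading**

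Assume no deaths or losses, so that Kaplan-Meier equals the simple proportion. Count patients with progression:

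- *a*: at W6 or W14 only
- *b*: at M6, resolved by M12
- *c*: at M6 and still at M12
- *d*: at M9 only
- *e*: new at M12

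Status at Vi: M6 events = b + c; M12 events = c + e.

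First progression up to Vi: M6 events = a + b + c; M12 events = a + b + c + d + e.

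Missed by the literal row: *a* at M6 and a + b + d at M12. Neither can be negative, so the literal row can only omit events.

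Reversal: M12 PFS exceeds M6 PFS on the literal row when c + e < b + c, that is when e < b. On the cumulative reading the M12 count is the M6 count plus d + e, so no reversal is possible. Both statements held in all 1,024 patterns with each count from 0 to 3.

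**4. Illustration (N = 24; all counts assumed)**

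| a, b, c, d, e | Status at Vi: M6 / M12 | First progression up to Vi: M6 / M12 |
|---|---|---|
| 0, 0, 2, 0, 2 | 22/24 = 91.7% / 20/24 = 83.3% | 91.7% / 83.3% |
| 1, 1, 1, 1, 1 | 22/24 = 91.7% / 22/24 = 91.7% | 21/24 = 87.5% / 19/24 = 79.2% |
| 2, 2, 1, 1, 1 | 21/24 = 87.5% / 22/24 = 91.7% | 19/24 = 79.2% / 17/24 = 70.8% |

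With no transient progression (first row) the readings agree. In the third row the literal reading shows PFS rising between M6 and M12.

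**5. Size per missed event**

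1/24 = 4.2 points. PFS is analysed in the FAS, which requires a completed first cycle and a Week 6 response evaluation (SAP 11.1) and so may be smaller than 24. With 21 patients, 1/21 = 4.8 points.

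**The case against.** The strongest reply is that Vi is an analysis horizon rather than a visit at which status is read. The introduction, the timing rule and the table label are all cumulative, and the overall survival row carries the same tag with an explicitly cumulative meaning. Appendix 17.1 covers all five visits, so first progression can be derived, and Listing 16.2.5.4 shows response at each visit. On that reading nothing is missed and no reversal can occur. This stands as far as it goes: the text does not settle on a status-only rule. It does not remove the defect, because the one row that determines the event still says something else.

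Three stronger conclusions are tempting, and the documents do not support them.

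- *A reader might infer that FFS is biased in the same way, because "or other medications specified into the CRF (Vi_RESP_FAIL and or Vi_RESP_FAIL_S") is also indexed by M6 and M12.* The FFS components are death, malignancy and the start of a new systemic treatment. All can be dated, and they are counted from first infusion to Vi. The look-back period of the CRF field is not stated, and nothing shows that it leaves out earlier failures.
- *A reader might infer that the PFS curve must be flat before M6.* The event is dated at first progression, so a patient with progression at M6 that was first seen at W6 can have an event time at W6.
- *A reader might infer that PFS is certain to be overstated.* That depends on the literal reading being programmed and on transient progressions occurring.

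It is also fair to say that PFS is secondary and descriptive, with no test attached (SAP 12.4.3.4).

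**Conclusion.** The concern holds for PFS, as an event row that contradicts its own section. Programmed literally, it can only raise PFS, and it lets the separate M6 and M12 analyses disagree in a way that a time-to-first-event endpoint cannot. Programmed cumulatively, it does no harm. The size is about 4.2 points per missed event if 24 patients are analysed, and more if the FAS is smaller. The number of transient progressors is unknown, so the total effect cannot be stated. No primary conclusion depends on it, but the row should be corrected because it can give a wrong estimate of a named endpoint. For FFS, the most that can be asked is confirmation of what the CRF field covers.

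**What to change.** Replace the PFS event row with: *Yes, if global progressive disease (Appendix 17.1) is met at any assessment (W6, W14, M6, M9, M12 or drop-out visit) after first ATO infusion and on or before Vi; dated at the first such assessment.* Add that every M6 event is also an M12 event. For FFS, confirm that Vi_RESP_FAIL covers failures recorded at earlier visits.

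The cost is one sentence and minor programming. Form A is already scheduled at all five visits and at drop-out (Protocol Table 2). Appendix 17.1 does not name the drop-out visit, so its visit list needs that addition. Reported PFS may be lower than under the literal row.

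One related matter needs its own decision. SAP 8.2.2 defines PFS by relapse or progression of the original disease, whereas 11.4.2.2 b) uses chronic GvHD organ progression and does not list death as an event. The wording above assumes that the organ-progression definition is kept.

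### The event-time formulas for FFS, PFS and OS in SAP 11.4.2.2 are printed with the two dates reversed, against their own labels and the SAP's OS definition

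*SAP*

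**What the plan says.** SAP 11.4.2.2 has three derivation tables: a) failure-free survival, b) progression-free survival and c) overall survival. Each gives a rule in words and then a formula for patients with an event.

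- **Overall survival.** The row is labelled "Time calculation from first ATO infusion to death at Vi". The rule in words is "the difference of date between the first ATO infusion and the date of death (expressed in months) is calculated". The formula is "Date of first ATO infusion – Date of death)/30.5".
- **Failure-free survival.** The rule in words is "the difference of date between the first ATO infusion and the first failure (expressed in months) is calculated". The formula subtracts the date of first failure from the date of first infusion and divides by 30.5.
- **Progression-free survival.** The formula has the same form, with the date of first progression. The row label still refers to failure, which suggests that the block was copied from a).

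For patients without an event, all three tables describe the time in words only, as the difference between first infusion and the visit Vi. No formula is printed.

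SAP 8.2.2 states the target quantity for overall survival: "OS is defined as the time from first infusion of ATO to death, regardless of the cause".

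**The concern.** A survival time is the later date minus the earlier one. All three formulas put the earlier date first, so a program that follows them literally produces negative durations for patients with events. Kaplan-Meier estimation cannot use such times. Depending on how they are handled, the events either fall before time zero in reversed order or drop out as invalid.

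The variable feeds every planned Kaplan-Meier figure: three endpoints x two time points (M6, M12) x two populations (FAS, PP) = 12 figures in the SAP 14.2 list. These are secondary endpoints named in the protocol. A derivation rule in an SAP should also give the right answer when a second programmer follows it without interpretation.

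**Working it through.** **1. Direction of the interval.** The overall survival event flag is "Yes, if the death occurs between the first ATO infusion and Vi". A counted death therefore falls on or after the infusion date, and infusion minus death is zero or negative. The same holds for failure and progression, which are described as occurring between first infusion and Vi.

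**2. Order used elsewhere in the SAP.** Section 11.3.1 computes cycle 1 onset minus GvHD assessment date, and cycle 2 onset minus cycle 1 onset. Section 11.3.2 computes prednisone onset minus assessment date. All are later minus earlier, so the reversal is not a convention of this SAP.

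**3. Sign and size.** Days from infusion divided by 30.5:

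| Event on day | As printed (months) | Dates in the right order (months) |
|---|---|---|
| 0 | 0 | 0 |
| 30 | -0.98 | +0.98 |
| 61 | -2.00 | +2.00 |
| 183 | -6.00 | +6.00 |
| 365 | -11.97 | +11.97 |

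Only the sign is wrong. An event on the infusion day itself gives 0 either way.

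**4. Effect on a Kaplan-Meier curve.** The documents give no survival figures, so there is nothing to reproduce. The data below are assumed for illustration: 24 patients with events at 2, 4, 5, 7, 9 and 11 months. Censored times are taken as positive, because the wording does not give them a sign.

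*Case A: the other 18 censored at 12 months.*
- Right order: S(6) = 21/24 = 0.875 and S(12) = 18/24 = 0.750.
- As printed: the steps fall at -11, -9, -7, -5, -4 and -2. The curve is already at 18/24 = 0.750 at time zero and stays flat. The number at risk at time zero is 18 instead of 24. The value at month 12 agrees; the value at month 6 does not (0.750 against 0.875).

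*Case B: 4 of the 18 censored at 3 months.*
- Right order: S(6) = 23/24 x 18/19 x 17/18 = 0.858, and S(12) = S(6) x 16/17 x 15/16 x 14/15 = 0.706.
- As printed: 0.750 from time zero onwards, because the four early censorings no longer come before any event.

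*Separate M6 analysis (three events by month 6, event-free patients censored no later than M6).*
- Case A: 21/24 = 0.875 either way as the final value.
- Case B: 0.858 in the right order against 21/24 = 0.875 as printed.

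*If negative times are discarded as invalid:* 18 patients and no events remain in either case, so the curve is flat at 1.00.

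*If the reversed order is also applied to censored times:* in case A the 18 censored patients leave at -12, before any event. The six events then exhaust the remaining six patients, and the curve falls to 0.

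**5. What does not depend on the sign.** The tables planned in 11.4.2.2 report numbers and percentages of events and of censored patients. They use the event flag, so they change only if records are discarded. The primary endpoint, response at M6, does not use this variable.

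**The case against.** The strongest reply is that nobody would be misled. The row label, the rule in words and SAP 8.2.2 all point forward from infusion to event. The magnitude is right, no alternative analysis is left open, and negative durations would be noticed at programming or quality control. The analyses are descriptive, with no survival test or decision rule. The numerical contrasts come from assumed data, and in case A the month 12 value does not change.

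Most of this stands. It limits how likely harm is and how serious the point is. It does not make the printed rule correct. The wording about a difference of dates carries no sign, so the formula is the only explicit instruction for event times, and it is wrong in three places. A programmer who silently reverses it departs from the written plan, while SAP 12.5 requires changes to the planned analyses to be documented.

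A reader might infer that the trial's survival curves are wrong, or that every planned survival result depends on the error. The documents do not support either reading. They contain a plan and no programmed output, and the event and censored counts do not use the sign.

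**Conclusion.** The subtraction order is reversed in SAP 11.4.2.2 a), b) and c), and this contradicts the variable labels, the overall survival definition in SAP 8.2.2 and the date order used elsewhere in the SAP. If programmed as printed, every event after the infusion day gets a negative time and the 12 planned Kaplan-Meier figures would be invalid. The size of the distortion depends on the data and on how software treats negative times. In the assumed examples, the month 12 estimate ranges from unchanged (0.750), through 0.750 against a correct 0.706, to 1.00 if negative times are dropped.

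This is a minor but real error in descriptive secondary analyses. The intended direction can be recovered from the text, and the primary endpoint is untouched.

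A related gap does bear on the curves and is not settled by the wording. Section 11.4.2.2 measures event-free patients to Vi, whereas section 12.4.3.2 censors those who leave early at their last information date. Cases A and B show that early censoring moves the estimate.

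**What to change.** 1. In 11.4.2.2 a), b) and c), replace the formula by (event date - date of first ATO infusion)/30.5.
2. Print the matching formula for event-free patients: (censoring date - date of first ATO infusion)/30.5.
3. Define the censoring date once, reconciling 11.4.2.2 with 12.4.3.2. The earlier of the Vi date and the last information date would be one way to satisfy both.
4. Correct the row label in b), which refers to failure instead of progression.
5. Add a programming check that all times are zero or greater.
6. If the survival programs have already been run, confirm which direction was used and record it in the clinical study report.

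The cost is three corrected formulas, one added formula, one definition and one check. No new data are needed, and neither the sample size nor the primary analysis changes.
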